### **6.2.8 Discharge from the Study Center**

A patient will be allowed to leave the study center 6-8 hours after the ANB020/placebo administration at the study center and completion of study-specific procedures providing that:

- No AEs have been reported during the study visit.
- The patient responds in the affirmative when asked if they are feeling well.

If any of these conditions are not met, then the patient will only be allowed to leave the study center with the authorization of the Investigator or appropriately qualified delegate.

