**Table 4.1 Schedule of Events**

Assessment Days	Screening 7-21 days prior to Day 1	Day 1	Day 2	Day 5	Day 14	Day 15	Follow-Up(30 days) Weekly Telephonic Contacts	EOS Day 45	EOS Day 46 n	ET f,p
General Assessments										
Informed Consent	X q	X a								
Medical History/Demographics	X									
Inclusion/Exclusion Criteria	X	X								
Oral Peanut Food Challenge (BPCFC)	X				X	X l,k		X l	X l,o	
Stanford University Only: Ex vivo Peanut Challenge Assay (whole blood) e	X		X	X						
Skin Prick Test and ImmunoCAP Testing	X h									
Safety Assessments										
Physical Examination b	X				X	X l		X	X l	X
Safety Laboratory c	X	X	X		X			X		X
Vital Signs b	X	X	X	X	X	X		X	X l	X
Spirometry or Peak Flow for Patients with History of Asthma i	X				X	X l,j		X l	X l,j	
Urinalysis	X	X	X		X				X	
Serum Pregnancy Test (WOCBP Only)	X	X			X			X		X
FSH m	X l									
12-Lead ECG	X							X		X
Concomitant Medications	X	X	X	X	X	X	X	X	X l	X
Adverse Events	X	X	X	X	X	X	X	X	X l	X
Clinical Observations										
Clinician and Patient Reported Outcomes (OFC Symptom Scoring Assessment Tool )	X				X	X l		X	X l	
PK/Biomarker Assessments										
Samples for PK d		X	X	X		X k		X		X
Serum Sampling for Biomarkers Cytokines e (IL-33, IL-4, IL-5, IL-9, IL-13, sST2)	X		X	X		X k				
Whole Blood for Leukocytes e	X g		X g	X		X k		X g		X g
IP administration										
Administration of ANB020 or Placebo		X								

Abbreviations: BPCFC = Blind placebo-controlled food challenge; ECG = electrocardiogram; EOS: End of Study; ET = Early Termination; FSH = follicle stimulating hormone; IL = interleukin; IP = investigational product; OFC = Oral Food Challenge; PK = pharmacokinetics; WOCBP = Women of childbearing potential

- a Confirm informed consent and continued willingness to participate.
- b See [Section 6.1.1](#) and [7.1.3](#) for the instructions to record vital signs, physical examination, and clinical evaluations using the OFC Symptom Scoring Assessment Tool during BPCFC.

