## 6.0 STUDY PROCEDURES

Study procedures will be performed as detailed in the Schedule of Events in [Table 4.1](#). Assessments scheduled on the day of IP administration must be performed prior to the IP infusion unless otherwise noted. All assessments will be performed on the day of the specified visit; however, a window period of +4 days is available for the Day 14/15 visit. Day 14 and Day 15 visits should remain consecutive. A window period of +/- 2 days can be implemented for visits occurring after completion of the Day 14/15 visit (i.e. Day 45). In addition, the blood sample collected from Stanford University patients for the ex vivo peanut challenge assay scheduled at Screening (prior to OFC), can be collected on Day 1 (prior to IP administration), if necessary.

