### 6.2.2 Day 1 (Randomization)

On Day 1, the patients will be randomized to receive either ANB020 or placebo in a 3:1 ratio (15 patients will receive ANB020 and 5 patients will receive placebo). If the blood sample collected from Stanford University patients for ex vivo peanut challenge assay was not collected at screening visit it must be collected on Day 1 (prior to IP administration). Additional Day 1 procedures will be carried out in accordance with the Schedule of Events in [Table 4.1](#). Patients with any ongoing AEs or SAEs at the time of scheduled discharge from the study center should remain at the study center until the Investigator has determined that these events have been resolved or deemed as not clinically significant by the Investigator.

### 6.2.3 Day 2 to Day 15

Patients will return to the study center on Days 2, 5, 14, and 15. Various assessments will be performed and blood samples will be collected. On Day 14, oral BPCFC will be administered and the symptoms will be monitored (See [Section 6.1.1](#) and [Section 6.1.2](#)). The oral BPCFC will be continued on Day 15 if the patient has received only the placebo challenge on Day 14 and the

blood samples scheduled on Day 15 will be collected on Day 16 (only applicable if the Investigator decides to complete the challenge in 2 days). Additional procedures will be carried out in accordance with the Schedule of Events in [Table 4.1](#).

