#### **6.2.7 Timing of Procedures**

There are times where the protocol requires more than one procedure to be completed at the same time point. In these instances, the following will apply to post-dose time points:

- The PK samples will take precedence over other procedures and will therefore be collected at the nominal time.

All safety assessments will be timed and performed relative to the start of dosing.

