### **7.1.1.1 Reporting of Adverse Events**

All AEs, regardless of severity occurred during the study (screening, treatment, or follow-up period) are to be recorded on the appropriate AE pages (either ‘serious’ or ‘non-serious’) in the eCRF. All AEs reported prior to IP administration will also be recorded on the medical history CRF page. The Investigator should complete all the details requested including dates of onset, severity, action taken, outcome, and relationship to the IP. Each event should be recorded separately.

The ANB020 or placebo infusion may be slowed or interrupted for patients experiencing infusion-related AEs. Following the infusion, all patients will be observed for fever, chills, rigors, hypotension, nausea, or other infusion-related AEs.

All SAEs (as described in [Section 7.1.1](#)) that occur after the patient has signed informed consent (including the protocol defined follow-up period), regardless of judged relationship to the IP, or after the study period, if considered serious and related to IP or to the patient’s participation in the study, must be reported to QuintilesIMS within 24 hours of the Investigator’s knowledge of the event. The SAE reporting will originate in the electronic data capture (EDC) system and an email will be sent to the designated responsible parties defined in the Safety Plan. The paper SAE form is in place as a back-up in the rare event that EDC is not accessible to the reporter of the SAE and the paper SAE form should be sent to [QLS\\[contact]](mailto:[contact]).

The following documents should be submitted to QuintilesIMS Safety:

- Serious Adverse Event Report Form.
- The following eCRFs or de-identified source documents:
  - Demographics page(s).
  - Medical history page(s).
  - Adverse event page(s).
  - Concomitant medication page(s).
  - Hospital discharge summary: If the patient is hospitalized because of or during the course of an SAE, then a copy of the hospital discharge.

Following are Investigator responsibilities:

- Record diagnosis instead of signs and symptoms when available using accepted medical terminology.

- The events recorded on the safety event report form must be consistent with the information entered on the respective CRFs.
- Include any relevant medical history, concurrent illnesses, and concomitant medicines.
- Include treatment(s) provided.
- The Investigator must assess causality at the time of the first SAE notification.

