### 7.1.3 Vital Signs, Physical Findings, and Other Safety Assessments

Vital signs will be measured, and physical examinations and ECGs will be performed at the time points indicated in the Schedule of Events (Table 4.1).

Vital signs include pulse rate, respiratory rate, body temperature, systolic BP, and diastolic BP. The physical examination includes evaluation of general appearance, head, eyes, ears, nose, and throat, and pulmonary, cardiovascular, gastrointestinal, renal/genitourological, endocrine (including thyroid), musculoskeletal/spinal, lymphatic, and dermatologic systems.

During the BPCFC, clinical evaluations using the OFC Symptom Scoring Assessment Tool and vital signs will be done before starting the initial placebo challenge, after completion of the final placebo challenge, before starting the initial peanut challenge, upon completion of the final peanut challenge, and 2 hours after completion of the final peanut challenge. Full physical examinations will be performed before starting the initial placebo food challenge and upon completion of the final peanut challenge (prior to discharge), and more frequent if deemed appropriate by the Investigator on the challenge day.

A standard 12-lead ECG will be performed by a qualified physician or nurse. The following parameters will be documented: HR, PR interval, QRS interval, QT interval, and QTc interval. The ECG will be reviewed by the Investigator or an authorized representative who is experienced in the evaluation of ECGs and assessed for clinical significance.

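### On the visible text, no vital signs are scheduled between the infusion and discharge on Day 1, although vital signs are a primary safety endpoint

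*Protocol*

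**What the plan says.** **Scheduling.** Table 4.1 marks vital signs once on Day 1, with no clock time and no split into predose and postdose. Section 7.1.3 gives Table 4.1 as the source of timing: "Vital signs will be measured, and physical examinations and ECGs will be performed at the time points indicated in the Schedule of Events". The footnote on the vital-signs row sends the reader to Sections 6.1.1 and 7.1.3 "for the instructions to record vital signs, physical examination, and clinical evaluations using the OFC Symptom Scoring Assessment Tool during BPCFC". Two general rules also apply. Section 6.0: "Assessments scheduled on the day of IP administration must be performed prior to the IP infusion unless otherwise noted". Section 6.2.7: "All safety assessments will be timed and performed relative to the start of dosing".

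**Observation and discharge.** Section 7.1.1.1: "Following the infusion, all patients will be observed for fever, chills, rigors, hypotension, nausea, or other infusion-related AEs". Section 6.2.8 lets a patient "leave the study center 6-8 hours after the ANB020/placebo administration at the study center and completion of study-specific procedures providing that" two conditions are met: no adverse event reported during the visit, and "The patient responds in the affirmative when asked if they are feeling well". If either fails, the Investigator or a qualified delegate must authorise departure. Under Section 6.2.2, patients with "ongoing AEs or SAEs at the time of scheduled discharge from the study center should remain at the study center until the Investigator" judges the events resolved or not clinically significant.

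**Role of the endpoint.** Safety and tolerability of the single dose is a primary objective (Section 3.1). Vital signs are on the list of primary safety endpoints (Synopsis and Section 9.4).

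**The concern.** Day 1 is the only dosing day. Section 2.4 warns that monoclonal antibodies can cause a reaction that includes fever and, at the severe end, hypotension. Temperature and blood pressure are both in the vital-sign set defined in Section 7.1.3, and they are the measurements that would show such a reaction. The plan does time vital signs elsewhere: each food-challenge visit has five fixed points (Sections 6.1.1 and 7.1.3).

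Two things are at stake. One is a change from predose on the infusion day, recorded in the same way in both arms at up to 3 centres. The other is a measured basis for discharge: a symptom-free fall in pressure or rise in temperature could satisfy both Section 6.2.8 conditions if nobody happened to measure it.

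**Working it through.** The plan gives no figure to reproduce. The check is a cross-reading followed by counts.

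**1. Is the Day 1 reading predose?** The Table 4.1 entry alone does not say. Section 6.0 supplies the default: before the infusion, unless noted otherwise. Possible sources of such a note:

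| Place | What it adds for Day 1 vital signs |
|---|---|
| Table 4.1, footnote b | Refers to food-challenge instructions; no challenge takes place on Day 1 |
| Section 7.1.3 | Refers back to Table 4.1; its own within-day times are for challenges only |
| Section 6.1.1 | Challenge times only |
| Section 6.2.2 | Refers to Table 4.1 |
| Section 6.2.7 | Timing relative to start of dosing, but no times; the one specific rule gives PK samples precedence |
| Section 7.1.1.1 | Observation after infusion; no measurement, time or frequency |
| Appendix 2 | Timed Day 1 draws, PK only |

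None sets a post-infusion reading, so the default stands. Table 4.1 also has no physical examination or ECG on Day 1 that might fill the interval.

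**2. Counts between start of infusion and discharge.**
- Scheduled vital-sign sets: 0.
- Scheduled PK draws: 3 (0.5 h, end of infusion, end of infusion + 3 h; Appendix 2).
- Time on site: the infusion lasts 1 h (Section 5.1) and discharge is 6-8 h after administration. The protocol does not say whether that runs from the start or the end, so the stay is between 6 h and 8 + 1 = 9 h from the start of infusion.

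**3. Next scheduled reading.** This is at the Day 2 visit, with no clock time. If it were taken with the Day 2 PK sample (24 h ± 2 h, Appendix 2), it would fall 24 − 2 = 22 to 24 + 2 = 26 h after the start of infusion. No text applies that PK window to vital signs, so the range is an assumption.

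**4. What the SAP does with readings a site takes on its own initiative.** SAP 3.2 takes its schedule from Table 4.1. SAP Section 6 leaves unscheduled or repeat measurements out of the descriptive statistics, but that sentence sits between PK rounding rules and PK/PD population rules, so its reach over vital signs is open to argument. SAP Section 22 keeps unscheduled visits out of the summaries, and Day 1 is a scheduled visit. SAP 18.5 summarises all available visits, and Table 14.3.6.1 has a time-point column with a placeholder. Such readings might therefore be listed but not summarised.

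**5. Volume with the change.** Two post-infusion sets × 20 patients = 40: 2 × 15 = 30 on ANB020 and 2 × 5 = 10 on placebo.

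**The case against.** The strongest reply is that the clinical work is already being done. Section 7.1.1.1 makes observation for fever and hypotension a duty for every patient, and neither can be reliably assessed without a thermometer and a cuff. The infusion can be slowed or interrupted (Section 5.6). Any reported adverse event, of any grade, ends automatic discharge, and ongoing events hold the patient at the centre. This stands. A reader might infer that patients go unmonitored after the infusion, or could be sent home with a recognised reaction; the documents do not support either reading.

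A second reply is that the timing is ambiguous rather than absent. Section 6.2.7 sits awkwardly with a blanket predose rule. Figure 4.1 is not reproduced in the text reviewed, and the annotated study book cited in the SAP references was not available; either could set times. This stands as a limit on confidence. It does not displace the Section 6.0 default, which is the only rule in the visible text that decides the matter.

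A third reply is that the lost summary is worth little. The SAP plans no statistical comparison of safety data (Section 18). With 15 and 5 patients, the 95% interval for a difference in means has a half-width of about 2.101 × √(1/15 + 1/5) = 1.08 SD. The Phase I single-dose study (64 healthy subjects, 32 by the IV route, doses to 750 mg) noted no change in vital signs. This too stands: a large yield should not be expected, and the value lies mainly in individual readings and the discharge check.

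**Conclusion.** The point holds as a cheap improvement to consider, with medium confidence. Under the Section 6.0 default, the schedule yields no vital signs between infusion and discharge for a primary safety endpoint, on a day when the patient is at the centre for at least 6 hours. What is lost is a uniform recorded set of post-infusion readings and an objective check before discharge. Adverse events found under Section 7.1.1.1 are not lost.

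Two stronger statements should be avoided. One is that site-initiated readings will certainly be dropped from the summaries; SAP Section 6 makes that possible, not certain. The other is that there is an established 22-26 h gap, which rests on a PK window borrowed for illustration. No reaction rate is assumed, because the documents give none for this population. The conclusion would change if Figure 4.1 or the study book already fixes post-infusion times; the sponsor could then answer by pointing to them.

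**What to change.** 1. **Table 4.1 and Section 7.1.3:** add a footnote and matching text scheduling Day 1 vital signs predose, at end of infusion and before discharge.
2. **Section 6.2.8:** require that the pre-discharge set is recorded and reviewed before the patient leaves. No separate rule for abnormal values is needed, since the existing adverse-event condition and the hold for ongoing events cover them.
3. **SAP 18.5 and Table 14.3.6.1:** name the three Day 1 readings as scheduled time points, with the predose reading as baseline. Saying so matters because the second sentence of SAP 6.2 works by date, and several Day 1 readings would then share the reference start date.

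The cost is a protocol amendment with IRB handling, an eCRF update, a short SAP change and two extra vital-sign sets per patient (about 40 in total). The end-of-infusion set coincides with a PK draw, which keeps precedence under Section 6.2.7. No extra visit is needed.

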## **7.0 SAFETY, PHARMACODYNAMIC, AND PHARMACOKINETIC ASSESSMENTS**

### **7.1 Safety**

Safety assessments will be based on medical review of AE reports, the results of physical examinations, and clinical laboratory tests. The incidence of observed AEs will be reviewed for potential significance and clinical importance. Patients with any ongoing AEs or SAEs at the time of scheduled discharge from the study center, should remain at the study center until the Investigator has determined that these events have been resolved or deemed as not clinically significant by the Investigator.

#### **7.1.1 Adverse Events**

The Investigator is responsible for recording all AEs observed during the study (screening, treatment, and follow-up) period.

Definition of AE: An AE is any untoward medical occurrence in a patient or clinical investigation patient administered a pharmaceutical product and which does not necessarily have a causal relationship with this treatment.

Definition of SAE: An SAE, experience or reaction, is any untoward medical occurrence (whether considered to be related to the IP or not) that at any dose:

- Results in death.
- Is life-threatening (the patient is at a risk of death at the time of the event; it does not refer to an event which hypothetically might have caused death if it were more severe).
- Requires inpatient hospitalization or prolongation of existing hospitalization: Hospital admissions and/or surgical operations planned before or during a study are not considered AEs if the illness or disease existed before the patient was enrolled in the study, provided that it did not deteriorate in an unexpected way during the study.
- Results in persistent or significant disability/incapacity.
- Is a congenital abnormality/birth defect.
- Other: Medically significant events, which do not meet any of the criteria above, but may jeopardize the patient and may require medical or surgical intervention to prevent one of the other serious outcomes listed in the definition above. Examples of such events are blood dyscrasias (e.g., neutropenia or anemia requiring blood transfusion, etc.) or convulsions that do not result in hospitalization.

An adverse drug reaction (ADR) is defined as all noxious and unintended responses to a medicinal product related to any dose.

An unexpected ADR is defined as any adverse reaction, the nature of which is not consistent with the applicable product information.

Each AE is to be evaluated for duration, severity, seriousness, and causal relationship to the IP. The action taken and the outcome must also be recorded.

### **Severity**

The severity of the AE will be characterized as “mild, moderate, or severe” according to the following definitions:

- Mild events are usually transient and do not interfere with the patient’s daily activities.
- Moderate events introduce a low level of inconvenience or concern to the patient and may interfere with daily activities.
- Severe events interrupt the patient’s usual daily activity.

### **Relationship**

The causal relationship between the IP and the AE has to be characterized as unrelated, unlikely, possible, probable, or unknown (unable to judge).

Events can be classified as “unrelated” if there is not a reasonable possibility that the IP caused the AE.

An “unlikely” relationship suggests that only a remote connection exists between the IP and the reported AE. Other conditions, including chronic illness, progression or expression of the disease state or reaction to concomitant medication, appear to explain the reported AE.

A “possible” relationship suggests that the association of the AE with the IP is unknown; however, the AE is not reasonably supported by other conditions.

A “probable” relationship suggests that a reasonable temporal sequence of the AE with drug administration exists and, in the Investigator’s clinical judgment, it is likely that a causal relationship exists between the drug administration and the AE, and other conditions (concurrent illness, progression or expression of disease state, or concomitant medication reactions) do not appear to explain the AE.

All efforts should be made to classify the AE according to the above categories. The category “unknown” (unable to judge) may be used only if the causality is not assessable, e.g., because of insufficient evidence, conflicting evidence, conflicting data, or poor documentation.

### **7.1.1.1 Reporting of Adverse Events**

All AEs, regardless of severity occurred during the study (screening, treatment, or follow-up period) are to be recorded on the appropriate AE pages (either ‘serious’ or ‘non-serious’) in the eCRF. All AEs reported prior to IP administration will also be recorded on the medical history CRF page. The Investigator should complete all the details requested including dates of onset, severity, action taken, outcome, and relationship to the IP. Each event should be recorded separately.

The ANB020 or placebo infusion may be slowed or interrupted for patients experiencing infusion-related AEs. Following the infusion, all patients will be observed for fever, chills, rigors, hypotension, nausea, or other infusion-related AEs.

All SAEs (as described in [Section 7.1.1](#)) that occur after the patient has signed informed consent (including the protocol defined follow-up period), regardless of judged relationship to the IP, or after the study period, if considered serious and related to IP or to the patient’s participation in the study, must be reported to QuintilesIMS within 24 hours of the Investigator’s knowledge of the event. The SAE reporting will originate in the electronic data capture (EDC) system and an email will be sent to the designated responsible parties defined in the Safety Plan. The paper SAE form is in place as a back-up in the rare event that EDC is not accessible to the reporter of the SAE and the paper SAE form should be sent to [QLS\\[contact]](mailto:[contact]).

The following documents should be submitted to QuintilesIMS Safety:

- Serious Adverse Event Report Form.
- The following eCRFs or de-identified source documents:
  - Demographics page(s).
  - Medical history page(s).
  - Adverse event page(s).
  - Concomitant medication page(s).
  - Hospital discharge summary: If the patient is hospitalized because of or during the course of an SAE, then a copy of the hospital discharge.

Following are Investigator responsibilities:

- Record diagnosis instead of signs and symptoms when available using accepted medical terminology.

- The events recorded on the safety event report form must be consistent with the information entered on the respective CRFs.
- Include any relevant medical history, concurrent illnesses, and concomitant medicines.
- Include treatment(s) provided.
- The Investigator must assess causality at the time of the first SAE notification.
- The Investigator is responsible for obtaining and forwarding or recording the details of the outcome of the SAE on the appropriate eCRF, as well as any other details which may be requested by AnaptysBio and/or QuintilesIMS in a timely manner:
  - Hospital records.
  - Medical records.
  - Data clarification.
  - Death certificate/autopsy results.
  - Events should be followed until they are resolved or stabilized, “Resolved with sequelae” will require specification of the sequelae.
  - For a fatal or life-threatening SAE, please call QuintilesIMS Safety Group (contact information is located on the SAE form), in addition to entering the SAE details in the eCRF.
  - The SAEs should continue to be reported for at least 5.5 half-lives of IP following last dose.
  - Queries on SAE reports will be generated when there is missing/discrepant information, or when there is a need for additional information to completely evaluate the report. All supplemental SAE information and or documentation is to be recorded on the appropriate eCRF and must be submitted upon request.

